7.5 Withdrawal of informed consent for donated biological samples

If a subject withdraws consent to the use of donated biological samples, the samples will be disposed of/destroyed, and the action documented. If samples are already analysed, AstraZeneca is not obliged to destroy the results of this research.

The Principal Investigator:

- Ensures subjects' withdrawal of informed consent to the use of donated samples is notified immediately to AstraZeneca
- Ensures that biological samples from that subject, if stored at the study site, are immediately identified, disposed of /destroyed, and the action documented.
- Ensures the laboratory(ies) holding the samples is/are informed about the withdrawn consent immediately and that samples are disposed/destroyed, the action documented and the signed document returned to the study site.
- Ensures that the subject and AstraZeneca are informed about the sample disposal.

AstraZeneca ensures the central laboratory(ies) holding the samples is/are informed about the withdrawn consent immediately and that samples are disposed of/destroyed and the action documented and returned to the study site.

8. ETHICAL AND REGULATORY REQUIREMENTS

8.1 Ethical conduct of the study

The study will be performed in accordance with ethical principles that have their origin in the Declaration of Helsinki and are consistent with ICH/Good Clinical Practice, applicable regulatory requirements and the AstraZeneca policy on Bioethics and Human Biological Samples. The applicable regulatory requirements in Japan are 'Good Clinical Practice for Trials on Drugs (MHLW Ordinance No. 28, 27 March 1997, partially revised by MHLW Ordinance and their related notifications.

8.2 Subject data protection

The Master Informed Consent Form will explain that: Study data will be stored in a computer database, maintaining confidentiality in accordance with national data legislation. Subject data will be maintaining confidentiality in accordance with national data legislation. For data verification purposes, authorised representatives of AstraZeneca, a regulatory authority, an Ethics Committee may require direct access to parts of the hospital or practice records relevant to the study, including subjects' medical history. All data computer processed by AstraZeneca will be identified by study code and enrolment code (E-code).

8.3 Ethics and regulatory review

An Ethics Committee should approve the final study protocol, including the final version of the Informed Consent Form and any other written information and/or materials to be provided to the subjects. The Head of the study site will ensure the distribution of these documents to the applicable Ethics Committee, and to the study site staff.

The head of the study site should submit a notification of direction/determination as well as a copy of the IRB written approval to AstraZeneca before enrolment of any subject should into the study.

The Ethics Committee should approve all advertising used to recruit subjects for the study.

AstraZeneca should approve any modifications to the Informed Consent Form that are needed to meet local requirements.

The protocol should be re-approved by the IRB annually. The Principal Investigator should submit progress reports to the IRB via the head of the study site at the time of the protocol re-approval.

Before enrolment of any subject into the study, the final study protocol, including the final version of the Informed Consent Form, is approved by the national regulatory authority or a notification to the national regulatory authority is done, according to local regulations.

AstraZeneca will handle the distribution of any of these documents to the national regulatory authorities.

AstraZeneca will provide Regulatory Authorities, Ethics Committees and Principal Investigators with safety updates/reports according to local requirements.

8.4 Informed consent

The Principal Investigator(s) at each centre will:

- Ensure each subject is given full and adequate oral and written information about the nature, purpose, possible risk and benefit of the study.

- Ensure each subject is notified that they are free to discontinue from the study at any time.
- Ensure that each subject is given the opportunity to ask questions and allowed time to consider the information provided.
- Ensure each subject provides signed and dated informed consent before conducting any procedure specifically for the study.
- Ensure the original, signed Informed Consent Form(s) is/are stored in the Investigator's Study File.
- Ensure a copy of the signed Informed Consent Form is given to the subject.
- Ensure that any incentives for subjects who participate in the study as well as any provisions for subjects harmed as a consequence of study participation are described in the informed consent form that is approved by an Ethics Committee.

If any new information on the study medication becomes available which may influence the decision of the subject to continue the study, the investigator(s) should inform the subject of such information immediately, record this in a written form, and confirm with the subject if he or she wishes to continue the participation in the study. In addition, if the investigator(s) deem it necessary to revise the Informed Consent Form, they should revise it immediately (Refer to Section 8.5). The investigator(s) should re-explain the subjects using updated Informed Consent Form even if although the subjects have already been informed of the new information verbally. Written informed consent to continue participation in the study should be provided separately.

8.5 Changes to the protocol and informed consent form

Study procedures will not be changed without the mutual agreement of the Principal Investigator and AstraZeneca. If it is necessary for the study protocol to be amended, the amendment should be submitted to the Head of the Study Site and be approved by its IRB. If applicable, AstraZeneca should submit a notification to the regulatory authority before it is implemented. If a protocol amendment requires a change to a particular centre's Informed Consent Form, then AstraZeneca and the centre's IRB should be notified. Approval of the revised Informed Consent Form by AstraZeneca and by the IRB is required before the revised form is used. If an administrative change is required, such a change should be notified to or approved by each IRB according to local requirements.

8.6 Audits and inspections

Authorised representatives of AstraZeneca, a regulatory authority, or an Ethics Committee may perform audits or inspections at the centre, including source data verification. The purpose of an audit or inspection is to systematically and independently examine all study-related activities and documents, to determine whether these activities were conducted, and data were recorded, analysed, and accurately reported according to the protocol, Good Clinical

Practice (GCP), guidelines of the International Conference on Harmonisation (ICH), and any applicable regulatory requirements. The investigator will contact AstraZeneca immediately if contacted by a regulatory agency about an inspection at the centre.

All study data may undergo a reliability review and onsite-GCP inspection by the regulatory authorities.

9. STUDY MANAGEMENT BY ASTRAZENECA

9.1 Pre-study activities

Before the first subject is entered into the study, it is necessary for a representative of AstraZeneca to visit the investigational study site to:

- Determine the adequacy of the facilities
- Determine availability of appropriate subjects for the study
- Discuss with the investigator(s) (and other personnel involved with the study) their responsibilities with regard to protocol adherence, and the responsibilities of AstraZeneca or its representatives. This will be documented in the contract between AstraZeneca and the head of the investigational study site.

9.2 Training of study site personnel

Before the first subject is entered into the study, an AstraZeneca representative will review and discuss the requirements of the Clinical Study Protocol and related documents with the investigational staff and also train them in any study specific procedures and the WBDC system(s) utilised.

The Principal Investigator will ensure that appropriate training relevant to the study is given to all of these staff, and that any new information relevant to the performance of this study is forwarded to the staff involved.

The Principal Investigator will maintain a record of all individuals involved in the study (medical, nursing and other staff).

9.3 Monitoring of the study

During the study, an AstraZeneca representative will have regular contacts with the study site, including visits to:

- Provide information and support to the investigator(s).
- Confirm that facilities remain acceptable.

- Confirm that the investigational team is adhering to the protocol, that data are being accurately and timely recorded in the CRFs, that biological samples are handled in accordance with the Laboratory Manual and that investigational product accountability checks are being performed.
- Perform source data verification (a comparison of the data in the CRFs with the subject's medical records at the hospital or practice, and other records relevant to the study) including verification of informed consent of participating subjects. This will require direct access to all original records for each subject (eg, clinic charts).
- Ensure withdrawal of informed consent to the use of the subject's biological samples is reported and biological samples are identified and disposed of/destroyed accordingly, and the action is documented, and reported to the subject.

The AstraZeneca representative will be available between visits if the investigator(s) or other staff at the centre needs information and advice about the study conduct.

9.3.1 Source data

Source data are any data generated as a result of the subject's inclusion in the study (including run-in and/or follow up related to the study) and includes all related medical examinations and other records. Original data recorded on the CRFs and regarded as source data are specified in the Clinical Study Agreement between AstraZeneca and the investigator.

9.3.2 Direct access to source data in Japan

The Head of the institution and the investigator(s) will cooperate for monitoring and audit by AstraZeneca, and accept inspection by the IRB or regulatory authorities. All study documents such as raw data will be open for direct access to source data at the request of the monitor and the auditor of AstraZeneca, the IRB, or regulatory authorities.

The monitor(s) will verify data from the CRFs against source data before collecting the CRFs to ensure accuracy and completeness of documentation, and assure that the investigator(s) has submitted the CRFs to AstraZeneca. If the investigator wishes to amend the collected CRFs, the monitor will ensure that the investigator(s) has documented the amendment in writing (signed and dated) and provided this to AstraZeneca.

9.4 Study agreements

The Principal Investigator at each/the centre should comply with all the terms, conditions, and obligations of the Clinical Study Agreement for this study. In the event of any inconsistency between this Clinical Study Protocol and the Clinical Study Agreement, the terms of Clinical Study Protocol shall prevail with respect to the conduct of the study and the treatment of subjects and in all other respects, not relating to study conduct or treatment of subjects, the terms of the Clinical Study Agreement shall prevail.

Agreements between AstraZeneca and the Principal Investigator should be in place before any study-related procedures can take place, or subjects are enrolled.

9.4.1 Archiving of study documents

- (i) **Study files.** AstraZeneca will provide the Principal Investigator with a file in which to organise and retain all study-related documents. All study documents (including letters from AstraZeneca) should be retained in this file by the Principal Investigator. The monitor will regularly check the file to ensure that all relevant documents are retained. The contents of the file may be audited/inspected by AstraZeneca's auditor, regulatory authorities, or IRB.
- (ii) **Period of record retention.** The study site (and the Principal Investigator) will retain the essential documents specified in the ICH GCP (eg, source document such as medical records, contract, signed consent form). Essential documents should be retained at the study site for at least 15 years following completion of the study, or per regulatory obligations if longer, and thereafter destroyed only after agreement with AstraZeneca. However this is not always applied to those that are not preservable such as blood samples. In the event of any inconsistency between the above-mentioned contents and the contract with the study site, the contract shall prevail. These documents should be retained for a longer period however if needed by AstraZeneca, and the specific period and method of retention will be separately discussed between the study site and AstraZeneca. AstraZeneca should notify the head of the study site in writing when the study related records are no longer needed. The records should be managed by a responsible person appointed by the head of the study site.

9.4.2 Deviation from the clinical study protocol in Japan

Investigator(s) must not deviate from or make any changes to the protocol without documented agreement between the principal investigator and AstraZeneca or the IRB approval based on its deliberations. However, this shall not apply to cases where the deviation or change is necessary to avoid an immediate hazard to the patients or for other compelling medical reasons, or where the changes involve only logistical or administrative aspects of the clinical trial (e.g. changes to the organisation/structure of the sponsor, the name/department name of the medical institution, the address or phone number of the medical institution or the sponsor, the job title of the investigator, and monitors). In such case, the principal investigator must notify details of the deviation or change, the reason, and a proposed revision in the protocol if required, to AstraZeneca and the head of the study site and IRB via the head of the study site as soon as possible, in order to obtain their approval. A certificate of approval by the head of the study site as well as AstraZeneca should be obtained via the head of the study site.

The investigator(s) should document any deviation from the protocol regardless of their reasons. Only when the protocol was not followed in order to avoid an immediate hazard to the patients or for other medically compelling reason, the investigator should prepare and submit the records explaining the reasons thereof to the sponsor, and retain a copy of the records.

9.5 Study timetable and end of study

The end of the study is defined as "the last visit of the last subject undergoing the study".

The study may be terminated at individual centres if the study procedures are not being performed according to GCP, or if recruitment is slow. AstraZeneca may also terminate the entire study prematurely if concerns for safety arise within this study or in any other study with dapagliflozin.

9.5.1 Planned duration of the study

Study period (First Subject In – Last Subject Last Visit): August, 2009 – June 2010

Registration period: August, 2009 - January, 2010

9.5.2 Discontinuation or suspension of the whole study programme

If AstraZeneca decides to prematurely terminate or suspend the study, the investigator(s), the head of the institution, and regulatory authorities should receive written notification of the reasons for the premature termination or suspension.

The investigator(s) will immediately notify the decision to the subjects, give appropriate medical treatment; take necessary measures, and record treatment or measures provided on the source documents.

9.5.3 Completion of the study

Upon terminating the study, the investigator(s) will report in writing the completion of the study as well as the summary of the results to the head of the study site in accordance with the institution's rules. The head of the study site, who is informed of the termination by the investigator, will provide a written notification of the results to the IRB and AstraZeneca.

10. DATA MANAGEMENT BY ASTRAZENECA DATA MANAGEMENT CENTRE

Data management will be performed by AstraZeneca Data Management Centre staff.

The data collected through third party sources will be obtained and reconciled against study data.

Adverse events and medical/surgical history will be classified according to the terminology of the latest version the Medical Dictionary for Regulatory Activities (MedDRA). Medications will be classified according to the Bristol-Myers Squibb Drug Dictionary. All coding will be performed by the Medical Coding Team at Bristol-Myers Squibb.

Data queries will be raised for inconsistent, impossible or missing data. All entries to the study database will be available in an audit trail.

The data will be validated as defined in the Data Management Plan. Quality control procedures will be applied to each stage of data handling to ensure that all data are reliable and have been processed correctly.

When all data have been coded, validated, signed and locked, clean file will be declared. Any treatment revealing data may thereafter be added and the final database will be locked.

11. EVALUATION AND CALCULATION OF VARIABLES BY ASTRAZENECA

11.1 Calculation or derivation of efficacy variable(s)

Baseline is defined as the assessment performed at pre-dose on Week 0.

11.1.1 Beta-cell function and insulin resistance index

The beta-cell function and insulin resistance index will be calculated based on FPG and fasting plasma insulin using HOMA2.

The beta-cell function during an OGTT will be calculated using the insulinogenic index. The insulin sensitivity during an OGTT will be calculated using the Matsuda index or ISIcomp.

11.1.2 AUC from 0 to 180 minutes for postprandial glucose, insulin, and C-peptide response to an OGTT

The AUC from 0 to 180 minutes for postprandial glucose, insulin, and C-peptide response to an OGTT will be calculated using the trapezoidal rule.

11.2 Calculation or derivation of safety variable(s)

11.2.1 Other significant adverse events (OAE)

During the evaluation of the AE data, an AstraZeneca medically qualified expert will review the list of AEs that were not reported as SAEs and DAEs (Discontinuation of Investigational Product due to Adverse Event). Based on the expert's judgement, significant adverse events of particular clinical importance may, after consultation with the Global Patient Safety Physician, be considered OAEs and reported as such in the Clinical Study Report. A similar review of laboratory/vital signs/ECG data will be performed for identification of OAEs.

Examples of these are marked haematological and other laboratory abnormalities, and certain events that lead to intervention (other than those already classified as serious), dose reduction or significant additional treatment.

11.2.2 Creatinine clearance

To calculate Creatinine clearance using Cockcroft-Gault formula:

Male: $Crcl = [(140 - \text{age}) \times \text{weight (kg)}] / [72 \times \text{Scr}]$

Female: $\text{Ccr} = 0.85 \times [140 - \text{age}] \times \text{weight (kg)} / [72 \times \text{Scr}]$

11.2.3 Assessment of Renal Function and Calculation of the Glomerular Filtration Rate

Renal function must satisfy two criteria in this study for subjects who will receive placebo or study medication. These criteria are based on (1) Serum Creatinine (2) Calculated GFR

1. Serum Creatinine Criteria: To be eligible, a subject must have a Scr < 1.5 mg/dL (132.6 mmol/L) for males or < 1.4 mg/dL (123.8 mmol/L) for females.
2. GFR Criteria: To be eligible, a subject must also have a calculated GFR (Using Age, Sex, Race, and Scr) of > 60 ml/min/1.73 m². Appendix E has a listing of the serum creatinine values that (based on age, gender and race) would correspond to a GFR < 60 ml/min/1.73 m².

Glomerular filtration rate is considered to be the best method to measure the overall renal function in health and disease. The use of prediction formulas to calculate the GFR from serum creatinine and other variables, such as age gender and race is recommended by the National Kidney Foundation for the diagnosis and stratification of chronic renal diseases. The Modification of Diet in Renal Disease (MDRD) study equation can estimate highly accurately the GFR by including the subject's age gender, race and serum creatinine.

To calculate estimated GFR (eGFR) using MDRD:

Male: $\text{eGFR (mL/min/1.73m}^2) = 186.3 \times (\text{Scr})^{-1.154} \times (\text{Age})^{-0.203}$

Female: $\text{eGFR (mL/min/1.73m}^2) = \text{eGFR (Male)} \times 0.762$

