4.1 Inclusion criteria

For inclusion in the study subjects should fulfil the following criteria:

1. Provision of informed consent prior to any study specific procedures
2. Female and male aged 18 to ≤ 79 years in Japanese (If the patient is younger than 20 years old, signed informed consent by the patient's legal representative (a person who exercises parental authority for the patient, or if no one is applicable, a guardian; the patient's parent in principle) is necessary.)
3. Subjects with T2DM **AND** meet one of the following criterion:
 - Strictly treatment naïve subjects at enrolment, and HbA1c $\geq 7.0\%$ and $\leq 10\%$ at the enrolment visit. Strictly treatment naïve is defined as never received medical treatment for diabetes (insulin and/or oral anti-hyperglycaemic agents)
OR
 - Relatively treatment naïve subjects at enrolment, and HbA1c $\geq 7.0\%$ and $\leq 10\%$ at the enrolment visit. Relatively treatment naïve is defined as received medical treatment for diabetes for less than 30 days since diagnosis. In addition, during the 30-day period prior to enrolment did not receive oral anti-hyperglycemic medication for more than 3 consecutive or more than 7 non-consecutive days. Subjects also should not have a history of insulin therapy within 2 weeks of enrolment (with the exception of insulin therapy during a hospitalization for other causes or use in gestational diabetes)
OR
 - Subjects treated with anti-diabetic medication prior to enrolment, and HbA1c $\geq 7.0\%$ and $\leq 10\%$ at the enrolment visit. Subjects treated with anti-diabetic medication prior to enrolment is defined as previously treated with anti-diabetic medication but have not been treated within 6 weeks of enrolment
OR

- Subjects treated up to enrolment with a single oral anti-hyperglycaemic agent or with two agents with less than half of the approved maximal dose for each agent, HbA1c \leq 8% at the enrolment visit, and FPG \leq 240mg/dl at the enrolment visit
4. Fasting C-peptide $>$ 1.0 ng/mL (0.33 nmol/L) at the enrolment visit
 5. BMI \leq 40 kg/m² at the enrolment visit
 6. Scr $<$ 1.5 mg/dL (132.6 μ mol/L) for male subjects and $<$ 1.4 mg/dL (123.8 μ mol/L) for female subjects and glomerular filtration rate (GFR) calculated by the Modification in Diet in Renal Disease (MDRD) formula $>$ 60 mL/min/1.73 m² at the enrolment visit.
 7. No overt proteinuria defined as Spot urine Microalbumin/Cr ratio of $<$ 300 mg/g at the enrolment visit.

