1. SERUM CREATININE EXCLUSION

Table 1 (Serum creatinine (Scr) in mg/dL) is derived from combining:

1. Metformin exclusion criteria for serum creatinine based on gender which would exclude a subject from the study. **AND**
2. Serum creatinine values based on subject's age, gender and race which would exclude the subject from the study because the GFR (as calculated by Simplified Modification in Diet and Renal Disease (MDRD) formula ([Rigalleau et al 2005](#), [Levey et al 1999](#))) is ≤ 60 mL/min/1.73 m².

Table 1 Serum creatinine

Age (years)	Male Scr (mg/dL)	Female Scr (mg/dL)
18	1.5	1.3
19	1.5	1.3
20	1.5	1.3
21	1.5	1.2
22	1.5	1.2
23	1.5	1.2
24	1.5	1.2
25	1.5	1.2
26	1.5	1.2
27	1.5	1.2
28	1.5	1.2
29	1.5	1.2
30	1.5	1.2
31	1.5	1.2
32	1.5	1.2
33	1.5	1.2
34	1.5	1.1
35	1.5	1.1
36	1.5	1.1
37	1.5	1.1
38	1.4	1.1

Table 1 **Serum creatinine**

Age (years)	Male Scr (mg/dL)	Female Scr (mg/dL)
39	1.4	1.1
40	1.4	1.1
41	1.4	1.1
42	1.4	1.1
43	1.4	1.1
44	1.4	1.1
45	1.4	1.1
46	1.4	1.1
47	1.4	1.1
48	1.4	1.1
49	1.4	1.1
50	1.4	1.1
51	1.4	1.1
52	1.4	1.1
53	1.4	1.1
54	1.4	1.1
55	1.4	1.1
56	1.4	1.1
57	1.3	1.1
58	1.3	1.1
59	1.3	1.0
60	1.3	1.0
61	1.3	1.0
62	1.3	1.0
63	1.3	1.0
64	1.3	1.0
65	1.3	1.0
66	1.3	1.0
67	1.3	1.0
68	1.3	1.0
69	1.3	1.0

Table 1 **Serum creatinine**

Age (years)	Male Scr (mg/dL)	Female Scr (mg/dL)
70	1.3	1.0
71	1.3	1.0
72	1.3	1.0
73	1.3	1.0
74	1.3	1.0
75	1.3	1.0
76	1.3	1.0
77	1.3	1.0
78	1.3	1.0
79	1.3	1.0

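### The eGFR formula in Section 11.2.3 does not generate the Appendix E creatinine table: at 22 of 62 female ages (16 if eGFR is rounded) it admits women whom the table excludes

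*Protocol*

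**What the plan says.** Inclusion criterion 6 (Section 4.1) requires, besides a serum creatinine limit, a "glomerular filtration rate (GFR) calculated by the Modification in Diet in Renal Disease (MDRD) formula" above 60 mL/min/1.73 m² at enrolment. Section 4 allows no exceptions to the selection criteria.

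Section 11.2.3 repeats the rule: "a subject must also have a calculated GFR (Using Age, Sex, Race, and Scr) of > 60 ml/min/1.73 m²". It prints the male formula with the core "186.3 \times (\text{Scr})^{-1.154} \times (\text{Age})^{-0.203" and the female formula as "eGFR (Male)} \times 0.762". It then ties the formula to the table: "Appendix E has a listing of the serum creatinine values that (based on age, gender and race) would correspond to a GFR" below 60.

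Appendix E gives one creatinine value per year of age (18 to 79) and sex. Its introduction calls them "Serum creatinine values based on subject's age, gender and race which would exclude the subject from the study because the GFR" by simplified MDRD is at or below 60. The female values are 1.3 mg/dL at ages 18-20, 1.2 at 21-33, 1.1 at 34-58 and 1.0 at 59-79. The male values are 1.5 at 18-37, 1.4 at 38-56 and 1.3 at 57-79.

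**The concern.** The formula and the table are presented as two expressions of one rule, so each tabulated value should be the lowest creatinine, in steps of 0.1 mg/dL, at which the formula falls to 60 or below. If it is not, a site that calculates and a site that looks up the table can decide differently about the same woman under a criterion that allows no exceptions. One of them then records either an incorrect enrolment, which Section 5.8.1 lists as a reason for discontinuation, or an unnecessary screen failure.

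Section 11.2.3 also stands under the derivation of safety variables. A female factor that differs from the one behind the table therefore shifts the level of every woman's reported eGFR relative to the basis used at screening.

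**Working it through.** **Inputs.** Section 11.2.3: constant 186.3, exponents -1.154 (creatinine, Scr) and -0.203 (age), female factor 0.762, eligible if above 60. Creatinine limits: below 1.5 mg/dL for men and below 1.4 for women. Appendix E, Table 1: 62 male and 62 female cut-offs.

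**Rule for rebuilding the table.** For each age, take the lowest Scr in 0.1 mg/dL steps with eGFR ≤ 60, capped at 1.5 (men) or 1.4 (women), and compare it with Appendix E. Do this with eGFR unrounded and with eGFR rounded to an integer.

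**Step 1: male column.** It does not use the female factor, so it tests the rebuilding rule. With 186.3 unrounded, 57 of 62 ages match; the misses are 38, 39 and 57-59. With integer rounding, 61 of 62 match; the miss is 57, where Scr 1.3 gives 60.57, which rounds to 61.

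**Step 2: female column as printed.** Age 59, Scr 1.0: 186.3 × 1.0^-1.154 × 59^-0.203 × 0.762 = 186.3 × 1 × 0.4370 × 0.762 = 62.0. The formula says eligible; the table says excluded. Other values at the tabulated cut-off:

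| Age | Appendix E Scr (mg/dL) | eGFR by Section 11.2.3 |
|---|---|---|
| 21 | 1.2 | 62.0 |
| 34 | 1.1 | 62.2 |
| 40 | 1.1 | 60.1 |
| 60 | 1.0 | 61.8 |
| 69 | 1.0 | 60.1 |
| 70 | 1.0 | 59.9 (agrees) |

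Unrounded, 22 of 62 ages disagree: 4 (21-24) + 7 (34-40) + 11 (59-69). With integer rounding, 16 disagree: 3 (21-23) + 5 (34-38) + 8 (59-66). At no female age does the reverse occur, that is, eGFR ≤ 60 at the next 0.1 step below the table value. Every female conflict therefore runs the same way.

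**Step 3: which element is responsible.** Number of mismatching ages:

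| Constant | Female factor | eGFR | Male | Female |
|---|---|---|---|---|
| 186.3 | 0.762 | unrounded | 5 | 22 |
| 186.3 | 0.762 | integer | 1 | 16 |
| 186.3 | 0.742 | unrounded | 5 | 6 |
| 186.3 | 0.742 | integer | 1 | 1 (age 34) |
| 186 | 0.762 | integer | 0 | 16 |
| 186 | 0.742 | unrounded | 4 | 5 |
| 186 | 0.742 | integer | 0 | 0 |

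The fifth row isolates the factor: the male column fits exactly and 16 female ages still fail. The last row reproduces all 124 table entries, but it needs all three settings together.

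**Step 4: factor implied by the female column.** A search in steps of 0.001 gives a single fitting value in each setting: 0.735 (186.3, unrounded), 0.741 (186.3, integer), 0.736 (186, unrounded) and 0.742 (186, integer). The ratio of printed to implied factor runs from 0.762/0.742 = 1.027 to 0.762/0.735 = 1.037. Near 60 that is 60 × 0.027 = 1.6 to 60 × 0.037 = 2.2 mL/min/1.73 m².

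**The case against.** The case for leaving this as a small matter is largely sound. The eligibility conflict needs a woman whose creatinine sits at the listed cut-off in particular age bands, and the formula value there is only 60.1 to 62.2. The separate creatinine limits apply either way. On-treatment renal discontinuation (Section 5.8.1, Appendix G) rests on the absolute rise in creatinine, not on eGFR. eGFR is not a primary, secondary or tertiary variable, and safety data are summarised descriptively. A constant multiplier cancels in percent change from baseline and applies to women in every arm. All of this limits the severity; none of it makes the formula and the table agree.

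A reader might infer that 0.762 is simply a misprint for 0.742 and that changing that one number repairs the protocol. The documents do not support this. With 186.3 kept, 0.742 still leaves 6 female and 5 male mismatches unrounded, or 1 and 1 rounded. The implied factor is a fitted value that moves with the constant and the rounding rule; the protocol does not state it. Nor is rounding the whole explanation for the male rows, since age 57 still conflicts with 186.3 after rounding.

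A reader might also infer that the formula admits women who fall below the proper renal limit. That assumes the table is right. Criterion 6 makes the calculated GFR the criterion and Section 11.2.3 describes Appendix E as a listing derived from it, so the documents do not say which one governs.

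Finally, the formula was read from a PDF by a program, and a misread digit cannot be ruled out from this text alone. Nothing points to one, but the printed factor should be checked against the signed protocol first.

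**Conclusion.** The contradiction is real. As printed, Section 11.2.3 and Appendix E give opposite eligibility decisions for women at the tabulated creatinine at 22 of 62 ages unrounded and 16 of 62 with integer rounding, always with the formula admitting and the table excluding. The female factor is the main cause; the leading constant and the unstated rounding rule account for the rest. Female eGFR derived by Section 11.2.3 is about 2.7-3.7% higher than Appendix E implies.

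This rests on creatinine being read in 0.1 mg/dL steps, as the table is built, and on the rebuilding rule that fits the male column. Severity is moderate to minor: a hard selection criterion and the level of a derived safety variable are affected, while the HbA1c analysis, the power and the creatinine-based discontinuation criteria are not.

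**What to change.** Reconcile Section 11.2.3 with Appendix E. The sponsor should confirm one leading constant, one female factor and one rounding rule for the comparison with 60, and correct whichever passage is wrong. The settings 186, 0.742 and integer rounding are a useful lead because together they reproduce the whole table, but the sponsor must confirm what was intended. If the printed formula is kept instead, Appendix E has to be regenerated from it, including the male ages that disagree. State which source decides if the two ever differ, and use the same formula for screening and for derived eGFR.

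The cost is a line or two in Section 11.2.3 or a regenerated table, plus a programming check that rebuilds all 124 entries. No change to sample size, visits or procedures is needed.
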